#### 9.3 Adverse events

#### 9.3.1 Investigator's responsibilities

Perform the verification of adverse events through questioning, relevant physical examination, assessment of evolution, as well as adequate medical and pharmacological management, resolution or outcome and final discharge following the definitions determined in national and international regulations. [45] [46] [47]

In case of adverse events or any event that puts the health and well-being of the patients at risk, appropriate medical attention will be provided, either at the research site or will be referred to the Hospital Center with greater resolving power with which the researcher and / or researcher site have medical care agreement. The researcher will notify the clinical monitor of the sponsor, according to the times established in the national and international regulations. In the case of serious adverse events, notify the sponsor and record the corresponding information in the case report form and in turn inform the Research Ethics Committee to the Research Committee.

The attention of the adverse events will be made according to the diagram of attention of the event (see Figure 3. Attention of the adverse event)

In the final report to be drafted by the Scientific Committee of the Department of Clinical Operations of Sophia Laboratories A.S. of V.C., will include the report of adverse events in compliance with current national and international regulations. [46] [47]

#### 9.3.1.1 Record of adverse events in the Case Report Form

The registry of adverse events considers the information concerning the identification data of the participating patient as code, age, sex, left eye, right eye.

Information about the type of adverse event, adverse reaction or suspected adverse reaction to the product under investigation or to the study medication, as appropriate. The date on which the adverse event occurs is reported, as well as in which the Investigator is aware of it, date of resolution or outcome, as applicable. The clinical diagnosis is indicated. Include in concomitant medications the therapy used for the pharmacological management of the adverse event, suspected adverse reaction, adverse reaction. Record the outcome or resolution of the event: patient recovered without sequelae, with sequelae, not recovered. Patient who presented death due to adverse reaction / adverse event, patient who presented death and it is judged that the drug could have contributed, patient who presented death and this is not related to the investigational product or drug, or indicate that it was not He knows what the consequence of the event is.

Consign information about the product or drug under investigation or the drug associated with the adverse event, adverse reaction or suspected adverse reaction. As applicable, information concerning generic denomination, distinctive denomination or product code in research and / or investigational medication should be recorded, as appropriate according to the methodological design of the study, this is relevant in the case of blinded studies or those where they use placebo as comparators, since there are circumstances that justify opening the cecum to determine if the adverse event, the adverse reaction or suspected adverse reaction may be attributable to the active agent, the combination of active agents, or the substance (s). s) pharmacologically inert (s), such as vehicles or additives, as appropriate the phase of clinical research in which the development of the drug is located. It will also be necessary to record the data concerning the batch number, manufacturer laboratory, expiration date, dosage, route of administration, start and end dates of administration and / or consumption, reason for the prescription; according to whether it is a Sophia Laboratories A.S. of V.C.

product or investigational medicine (protocol in which the patient currently participates) or is a medicine that the subject under investigation consumes for the treatment of basic concomitant diseases or used for the management of any sign or transient symptom that does not correspond to the Natural History of the pathology that motivated its entry into the research protocol.

CONFIDENTIAL

Record the withdrawal or maintenance of the medication, investigational product or investigational medication, as appropriate. Indicate if the adverse event disappears when the investigational product or investigational medication or suspicious medication is removed (to provoke the event). Also indicate if a dose adjustment is made, if the event changes in terms of intensity or seriousness, persistence of the reaction. It is important to indicate that in those patients who are exposed again to the investigational product, investigational medication or medication, which had previously been suspended, if the adverse reaction or adverse event reappears.

Regarding concomitant pharmacotherapy. Indicate the generic name, the dose, the route of administration, start and end dates of its use, as well as the reason for the prescription regardless if it is consistent with the information to prescribe or technical data sheet or is used outside the regulations or of what the local, national or international regulatory entity has authorized.

Concerning the relevant clinical antecedents. The analysis of the adverse event, adverse reaction or suspicion of adverse reaction considers the information previously reported, notwithstanding the clinical context in which said harmful phenomenon occurs in the participants of the clinical research protocol, it is of special interest, so that the information about previous ailments, hypersensitivity or allergy phenomena, previous surgical procedures, laboratory analysis or cabinet exams that have been practiced on the participant, etc., that the researcher deems convenient to mention may do so. If you have enough space in the case report format, you can complement the information of your clinical note in the clinical file.

#### 9.3.1.2 Follow up of adverse events

The IP will provide the attention and guidance of the EA that the participant presents until the outcome of the same, according to what is referred to in the following section.

#### 9.3.1.3 Procedures for a serious adverse event

The process of attention of the adverse event considers the following stages:

[figure not shown]

Figure 3. Attention to the adverse event

- A. During the development and conduct of the present clinical research, undesirable damaging events or adverse reactions, of medical implication, which do not necessarily have a causal relationship with the investigational product or investigational medication, may occur in the participant patient. These harmful phenomena can occur during the use of investigational drugs, unintentionally, at doses authorized for use in humans; by a local, national or international regulatory entity, whether for prophylaxis, diagnosis, treatment or for the modification of some physiological process. However, it can be suspected that the investigational product or the investigational drug or the placebo cause some unwanted clinical manifestation. Adverse events, adverse reactions or suspected adverse reactions to one or several medications can occur during the systematic evaluation of the participants (on the days when the clinical review is scheduled, according to the schedule of activities) or suddenly, as such way that,
- B. The investigator must be the first person to whom the patient reports that they have developed or presented a harmful clinical phenomenon during their participation in this research protocol.
- C. According to your clinical judgment; on the basis of the pertinent physical examination, interrogation, etc., as well as the analysis of the information available in the medical literature and that referred to in the investigator's manual, information to prescribe or technical data sheet of the comparator drug, the principal investigator determines the relevant attention of the event / harmful reaction; either
- D. In the research site or in the hospital with the greatest resolving power (1st, 2nd or 3rd level of medical attention). In such a way that, in case the patient is sent by the Investigator to a hospital, he / she attends by means of a reference system, it can be with an identification card that the patient belongs to the present investigation and there is an official number or folio, which pertains to the emergency care agreement with the health institution with the greatest resolving power, or a medical reference note issued by the principal investigator, so that appropriate care is given to the participating patient. It should be noted that the Study Sponsor, Sophia Laboratories, S.A. C.V., will pay the expenses for the medical care of the participating patient, only if the adverse event, adverse reaction or suspected adverse

- reaction to medication is associated or found in relation to the investigational product or investigational medication.
- E. Taking the clinical information collected, either during the care provided at the research site or provided by the treating physician (s) in the hospital, the principal investigator records the adverse event, suspected reaction adverse or adverse reaction to medication in your clinical note of the clinical record, indicating the seriousness, intensity (mild, moderate or severe), relationship with the investigational product or medication, as well as:
- F. The migration of the relevant data to the case report format and to its respective adverse event section; noting the pertinent information, already referred to in section 9.3.1.1., this in virtue of the fact that in cases of serious adverse events, which must be notified in less than 24 hours after the moment in which the principal investigator has knowledge of the same, the clinical monitor of the study is informed, so that in turn he / she informs the Scientific Committee and the Pharmacovigilance Department of the sponsor and later he / she informs the Research Ethics Committee. Regarding non-serious adverse events, these will be recorded and adequately addressed and the corresponding regulatory entity will be informed about the safety profile of the investigational product or investigational medication in the final report of the clinical trial.

The record of the outcome of the adverse event, suspicion of adverse reaction or adverse reaction to medication depends substantially on the follow-up that the principal investigator makes to the participant, since most of the harmful phenomena are expected, consult section of the safety profile in number 5.3 and in the researcher's manual, they are ophthalmic in nature, however there may be systemic alterations. Therefore, in the opinion of the researcher, the withdrawal or permanence of the participant will be considered, according to the provisions of section 6.2.2 Exclusion criteria of the present research protocol.

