# 6.4 Outcome variables

# 6.4.1 Security variables

# 6.4.1.1 Primary outcome variables

- Globet cell density
- Epithelial defects in cornea and conjunctiva.
- Presence of adverse events.

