6.4.3 Methods and scales to be used for the measurement of the variables

Variable	Unit	Symbolo	Type	Method of measurement	Normal value
Age	years		Continuous	Calculation from the day of birth	NA
Gender	Female/ Male	F/M	Nominal	Direct questioning	NA
Adverse events	Number of cases	n	Discreet	Conteo	NA
Intraocular presure	Milimeters of mercury	mmHg	Continuous	Goldman's applanation tonometry	11 - 21
Visual ability	Fraction	Snellen	Nominal	Chart	
Tear rupture time	Seconds	S	Continuous	Direct counting	> 10
Eye confort index	Points		Discreet	Questioning	
Adverse events	Present / Absent		Nominal	Comprehensive assessment	Absent
Goblet cell density	Cells per square milimeter	Cel/mm 	Continuous	Citology per impression	> 500 cell/mm
ital signs					
Heart rate	Beats per minute	lpm	Discreet	Auscultation	60 – 100
Breathing frequency	Breaths per minute	rpm	Discreet	Auscultation	12 – 24
Systemic blood pressure	Milimeters of mercury	mmHg	Continuous	Non-invasive auscultatory measurement	< 120 / 80
nterior segment					
Epithelial defects	Degrees		Discreet	Direct observation with green lysine and fluorescein stains	Oxford Scale
)phthalmologic signs an	d symptoms				
Conjunctival hiperemia	Normal / Very Light / Mild / Moderate / Severe		Ordinal	Direct observation.  Classification of Efron	Normal
Chemosis	Present / Away		Nominal	Direct observation	Absent
Burning	Severity: Absent, very mild, mild,		Nominal	Direct questioning	Absent

Version: 1.0

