#### 6.5.1.2 Basal visit

- Review of laboratory tests: refers to the review and analysis by the IP of the results of the BH, QS and PFH. See 6.4.3.12 Laboratory tests.
- Eligibility criteria: with the laboratory results, the subject's profile will be finalized for inclusion or not.
- Assignment: It refers to determining the intervention that the patient will follow during the study. It will be done according to section 7. Methods. Assignment of the intervention. This assignment will be made at the baseline visit (day 0) and will go along with the indication to start the treatment period the next day (day 1).
- Delivery of intervention: Refers to the delivery of the product under investigation to the patient of the study, by the research center. It will be done according to sections 6.3.1 Managed treatments and 6.3.4.1 Delivery and reception.
- Evaluation of variables: The data of the evaluation of the variables listed below can be taken from the scrutiny visit, as long as it does not exceed 7 days prior to this visit. It is the IP's prerogative to decide whether to use the information from the screening visit or to repeat the evaluations on this visit.
  - o Intraocular pressure
  - o Visual capacity
  - o TRL
  - o Epithelial defects (TF and TVL)
  - o Eye signs and symptoms
  - o Subsequent segment
  - o vital signs

- Eye comfort index: see 6.4.3.3 Eye comfort index
- Density of goblet cells (cytology per impression): see 6.4.3.2 Density of goblet cells (cytology per impression)
- Delivery of the subject's diary: It refers to the delivery by the IP to the subject, the subject's daily instrument.
- Delivery of quality questionnaire: It refers to the delivery by the IP to the subject, the quality questionnaire instrument.

#### 6.5.1.3 Visit 1

- Intervention delivery: see 6.5.1.2 Baseline visit
- Return of intervention: refers to the return of research products to the center by the research subject.
- Evaluation of adherence: refers to the assessment made by the IP according to section 6.3.2.1 Procedure to monitor adherence
- Adverse events: see 6.4.3.5 Presence of adverse events
- Intraocular pressure: see 6.4.3.6 Intraocular pressure
- Visual ability: see 6.4.3.1 Visual capacity
- TRL: see 6.4.3.10 Rupture time of the tear film
- Epithelial defects (TF and TVL): see 6.4.3.4.1 Stains
- Eye signs and symptoms: see 6.4.3.4 Eye surface integrity: and 6.4.3.9 Ocular symptomatology

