#### 8.3 Statistical methodology

#### 8.3.1 Analysis of primary and secondary outcome variables

The statistical analysis will be carried out by personnel of Sophia Laboratories. The statistical program SPSS version 19 (IBM Corporation, Armonk, NY, USA) will be used.

The designated personnel will be blinded to the intervention groups. The coding will be done using consecutive numbers for each intervention group.

The data will be collected and sorted in an excel sheet. Later they will be exported to the platform of the SPSS program. The variables will be categorized according to their nature.

The result of the continuous quantitative variables will be presented in measures of central tendency: mean, standard deviation and ranges. See Table 4. Scales to be used

The normal distribution of the results will be obtained by the Kolmogorov-Smirnov test.

The statistical analysis of the continuous **quantitative variables** to find significant differences (p) will be the following:

- Intra-group analysis: Wilcoxon rank test.
- Inter-group analysis: Mann-Whitney U test.

The level of difference to consider significance will be an alpha of 0.05 or less.

The result of nominal and ordinal qualitative variables will be presented in frequencies, proportions and percentages.

The statistical analysis to identify significant differences of the **qualitative variables** will be done creating 2x2 contingency tables and it will be carried out in the following way:

- Intra-group difference: McNemar or Pearson test.
- Difference between groups: test χ2 (Chi-square) of Pearson.

The level of difference to consider significance will be an alpha of 0.05 or less.

For the reporting of adverse events all eyes of those participants who were randomly assigned to an intervention group after the baseline visit will be considered. The results will be expressed in number of cases (eyes).

The final report of the results will be shown in tables or graphs, as appropriate.

It will be considered that the investigational drug is safe and tolerable when there are no clinical and statistical differences in all the variables of primary outcome, with respect to its comparator.

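### The primary adverse-event variable is summarised and tested only as a case count or present/absent, so the statistical part of the safe-and-tolerable rule cannot see a concentration of moderate, severe or serious events on PRO-167

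*Combined protocol and SAP*

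**What the plan says.** - **Primary variable.** Section 6.4.1.1 lists "Presence of adverse events" as a primary safety outcome, with no qualifier for grade, seriousness or cause.
- **Data type.** Table 4 (section 6.4.3) lists adverse events twice: once as a discrete variable with unit "Number of cases", and once as a nominal present/absent variable obtained by "Comprehensive assessment".
- **Analysis.** Section 8.3.1 counts adverse events in everyone randomised after the baseline visit, with the number of affected eyes as the result. Qualitative variables go into 2x2 tables; for the comparison of arms the plan gives "Difference between groups: test χ2 (Chi-square) of Pearson". Sections 8.3.1 to 8.3.3 do not mention intensity, seriousness, relationship or date of onset.
- **Decision rule.** Section 8.3.1 calls the product "safe and tolerable when there are no clinical and statistical differences in all the variables of primary outcome", relative to the comparator. It does not say what a clinical difference is.
- **What is recorded.** Under section 9.3.1.3 the investigator's clinical note gives, for each event, "indicating the seriousness, intensity (mild, moderate or severe), relationship with the investigational product or medication". Section 9.3.1.1 asks for the date on which the event occurred. Section 9.3.1.4 offers a four-category causality algorithm (Table 6), which the investigator may use but need not.
- **Start of exposure.** Assignment is on day 0 and, by section 6.5.1.2, "will go along with the indication to start the treatment period the next day (day 1").

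**The concern.** The trial records what is needed to judge how bad an event was and whether the product plausibly caused it. The specified analysis of the primary adverse-event variable then uses none of it. A mild transient event and a severe one each add one to the count. So does a reaction to impression cytology, anaesthetic, dyes or mydriasis. Because assignment comes a day before the first application and no onset rule is given, an event that precedes exposure is not clearly excluded.

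This matters because of the direction of the decision rule: absence of a difference is read as evidence of safety. If case counts are similar while moderate, severe or serious events sit mainly on PRO-167, the statistical part of the rule is satisfied. Whether the imbalance then counts against the product depends on what the sponsor regards as a clinical difference, and nothing in the plan fixes that before the data are seen.

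**Working it through.** No figure in the plan bears directly on this point. Section 6.6 supplies 12 subjects per arm with one eye each, and section 8.3.1 supplies the test and the 0.05 level. The documents give no adverse-event rates by grade, so **all event counts below are assumed**.

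**1. Can either specified form of the variable carry grade?** As present/absent, each eye is 0 or 1 whatever the intensity. As a number of cases, each event adds 1 whatever the intensity. Neither form can, whichever test is applied.

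**2. Equal counts, unequal harm.** Assume 4/12 on the comparator, all mild, and 4/12 on PRO-167, all severe. The 2x2 table is 4, 8 against 4, 8, and Pearson chi-square = 0, p = 1.00. Any equal pair gives the same result.

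**3. The same data restricted to severe events: 4/12 against 0/12.**
- Pearson without correction: 24 × (4×12 − 8×0)² / (12 × 12 × 4 × 20) = 55,296 / 11,520 = 4.80, p = 0.028.
- Fisher, two-sided: 2 × C(12,4) / C(24,4) = 2 × 495 / 10,626 = 0.093.
- The expected count of severe events is 2 per arm, so the uncorrected Pearson value should not be relied on alone.

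**4. Range around that example (12 per arm, none on the comparator).**

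| Severe events on PRO-167 | Pearson p | Fisher p |
|---|---|---|
| 3 | 0.064 | 0.22 |
| 4 | 0.028 | 0.093 |
| 5 | 0.012 | 0.037 |
| 6 | 0.005 | 0.014 |

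**5. Would a rank test on worst intensity solve it?** Score none 0, mild 1 and severe 3 for the data in step 2. Mann-Whitney gives U = 80, p = 0.60, because eight subjects in each arm are tied at zero. Replacing the count with an ordinal test would not reveal the pattern either. A table by intensity, read against a rule stated in advance, would.

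**The case against.** **The rule has two parts.** It asks for no clinical difference as well as no statistical one, and four severe events against four mild ones would ordinarily be called a clinical difference. A reader might infer from the case count that severe events on PRO-167 are cancelled by mild ones on the comparator. The text does not say so. Cancellation needs counts that happen to balance, and the clinical part leaves room to object. What remains is that this part has no criterion, so whether severity counts would be settled after the data are seen.

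**Severity and seriousness are used elsewhere.** Burning, foreign body sensation and itching are separate primary tolerability variables graded 0 to 4 (section 6.4.3.9). The eye comfort index asks about severity, and epithelial defects are graded on the Oxford scale. Serious events bear on elimination (6.2.3), unblinding (7.4.1) and early termination (9.2), and the final report must cover adverse events as regulations require (9.3.1). It would be wrong to say that the plan ignores severity, or that an equal adverse-event count alone yields a favourable conclusion, since every primary variable must agree. But the named symptoms do not cover other events, the 2x2 tables would collapse their grades, and none of the provisions on serious events defines how the final adverse-event comparison is judged.

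**Related events only.** A further inference is that the conclusion should rest on related events alone, because shared background events dilute a product difference. The dilution is arithmetically real. With assumed product-caused rates of 5% and 40%, and diluted rates 1 − (1 − p)(1 − b), Pearson power falls from 55% at b = 0 to 40%, 32%, 26% and 21% at b = 10%, 20%, 30% and 40%. That does not justify the switch. Causality is a judgement and the Table 6 algorithm is optional. The tubes differ in colour and lid shape, with only the secondary packaging identical (7.2), so attribution could be influenced by guessing the arm. The all-cause count is free of attribution. Sample size is also a large part of the weakness: at 5% against 20% with no background, power is 12% by Pearson and 4% by Fisher.

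**Conclusion.** The point holds in a limited form. The specified summary and test of the primary adverse-event variable are blind to intensity, seriousness and relationship, although all three are recorded. The statistical part of the rule can therefore show no difference when the worse events are concentrated on PRO-167, and the undefined clinical part is not a dependable safeguard.

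The size cannot be fixed from the documents. In the assumed example the count gives p = 1.0, while the severe events behind it split 4 to 0 (Pearson p = 0.028, Fisher p = 0.093). The example assumes exactly balanced totals and severe events in a third of one arm. It shows what the rule permits; it is not a forecast. With 3 against 0, neither Pearson nor Fisher reaches 0.05. The remedy is therefore descriptive tables with a stated interpretation. A different significance test would not be enough. The change is worth making because it affects what the trial can conclude.

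**What to change.** In section 8.3.1:

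1. Keep the all-cause adverse-event comparison between arms.
2. Add, per arm, the number of subjects with at least one event with onset on or after the first application, by worst intensity, by seriousness and by investigator-rated relationship. Require the relationship rating to be made by one stated method before any unblinding.
3. Compare moderate-or-severe events between arms, acknowledging the sparse counts, and list every severe or serious event by arm.
4. State that equal case counts alone do not support the safe-and-tolerable conclusion when moderate, severe or serious events are concentrated on PRO-167. This gives the clinical part of the rule some content in advance.
5. Do not make related-only events the sole basis of the conclusion.

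**Cost.** A few table rows and a short paragraph, with many small or empty cells. The case report form also needs a check. Section 9.3.1.3 places intensity and relationship in the clinical note and moves only the pertinent data to the form, by reference to section 9.3.1.1. The list there does not explicitly require an initial intensity grade or a causality category, so both should be confirmed as fields or added.
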